**Figure 2. Change in Systolic Blood Pressure during Trier Tasks**

satisfaction, social connectedness, and positive affect. In the waitlist control condition, no significant pre-post differences were present in any of the measures (Figure 3). Together, changes in mindfulness and self-compassion significantly predicted changes in depression, perceived stress, anxiety, and life satisfaction post-intervention ( $p < .05$ ).

Interestingly, at baseline, the link between stress and depression was stronger in those with low self-compassion compared to those with high self-compassion ( $\beta = -.31, p = .02$ ), indicating that these low self-compassionate adolescents may more easily become depressed when faced with stress. This finding, linked with findings from the first study, indicate that adolescents with low self-compassion are likely to be more easily stressed and therefore more easily depressed.

## Impact

Depression among adolescents is a prevalent and growing public health problem, the consequences of which have significant, long-term negative impacts for the individual, their families, and society. This innovative project, in a high-priority NCCIH area, will test the feasibility of a promising, novel, depression-prevention program adapted from a

**Figure 3. Change in Measures of Mindfulness, Self-compassion, and Dimensions of Emotional Wellbeing Measures**

successful adult Mindful Self-Compassion program. “Making Friends with Yourself” (MFY) will be refined and manualized, as well as feasibility-tested in an exploratory clinical trial, in adolescents who experience subsyndromal depression. It will also refine and test the comparative feasibility of an attention-control condition, piloted by our team in a mindfulness intervention for adolescents, to be adapted as a control intervention for this study. The measures selected for feasibility testing are theoretically meaningful and likely able to elucidate mechanisms by which either program impacts depressive symptoms. This information can be used to plan a future randomized trial. Reinforcing the potential impact is the collective extensive experience of the investigative team, including their experience with this population and in designing, implementing, and evaluating similar studies, as well as the supportive research environment of the University of North Carolina at Chapel Hill. If this manualized program proves acceptable, feasible and efficacious, there is great potential for its use in schools and other adolescent settings, thus amplifying its potential impact on reducing depression by enhancing the lives of adolescents and those who care for them.

### 3. STUDY DESIGN

---

[figure not shown]
In this study, we will refine and feasibility-test our mindful self-compassion program and an attention control program with a focus on adolescents who are experiencing subsyndromal depression. Subsyndromal to mild depression is defined as a score of at least 6 and 10 on the Quick Inventory of Depressive Symptoms (QIDS). The intervention program, called “Making Friends with Yourself” (MFY), implements mindfulness and self-compassion training. The control condition is a healthy lifestyle program for high-school aged adolescents. The control condition was developed by our team as an attention control group for our pilot adolescent mindfulness program and will be adapted for comparison with the MFY intervention. The 8-week programs will be piloted with a total of 80 adolescents. After completion of the 8-week program, the teens will participate in a post-group meeting to give feedback about program contents. Feedback will take place in the form of a focus group. Following the 8-week program, adolescents will be invited to participate in 6 monthly continuation sessions, designed to strengthen understanding of the topics presented in the 8-week course. Measures of depression, resilience, brooding, shame, mindfulness, and self-compassion will be obtained before the 8-week program, halfway through the program, after the 8-week program (intervention phase), and 3 and 36 weeks after program completion (continuation phase). Feedback from program participants will inform modifications and refinement of both programs.

Our primary goal is to examine the feasibility of implementing the program. After feasibility, the primary outcome to be explored will be the occurrence of incident major depressive disorder (MDD) with a secondary outcome to be explored being the trajectory of depressive symptoms over time (measured at baseline, program end and at 3 and 36 weeks post program) using the Short Mood and Feelings Questionnaire (SMFQ) administered to both the adolescent and a parent. Studies indicate high predictive validity in adolescent self-report of depression. The study psychologist will contact parents of teens with incident major depression, captured by the SMFQ at any of the scheduled time-points during the study, for referral to appropriate mental health care.

Randomization will be stratified by gender. As soon as 20 eligible adolescents qualify for enrollment, they will be allocated to either the MFY or healthy lifestyle groups, using a specially-designed computer program which utilizes a random number generator with a permuted block design to ensure that the

number of subjects allocated to the two arms over time are equal and to conceal the allocation. This will continue through 4 cohorts of adolescents (n=80). During participation, adolescents will keep a daily online diary, accessible from a cell phone, to document homework practice. Their engagement in the program will be captured by audiotaping program sessions. After each program's completion,

**Figure 4. Study Flow Diagram**

adolescents will participate in a focus group to give feedback about program contents. The adolescents will be invited to participate in 6 monthly continuation sessions, designed to strengthen understanding of the topics presented in the 8-week course. After the first two cohorts, a post-participation interview and questionnaire will capture additional feedback about the program.

The research assistant will transcribe audio-taped data from sessions and focus groups. The team will combine this data with feedback provided in diaries, interviews, and post-participation questionnaires. This will be analyzed using qualitative methods to inform revision of specific program components and the revision of detailed program manuals for future programs.

### 3.1: Recruitment, screening and consent

#### Recruitment

We will recruit adolescents who are experiencing subsyndromal depression in three ways:

- 1) Discussions with local guidance counselors and school personnel;
- 2) University-wide emails to the University community; and
- 3) Flyers posted in local high schools/community boards (a successful strategy in our preliminary studies).

Members of our study team have established relationships with personnel in several of the local school systems. This has been successful in meeting targeted recruitment numbers in previous research studies.

#### Screening

If an adolescent or parent is interested in the study, they can begin the screening process through the following ways:

- 1) **Phone:** interested participants can initially contact the study team by calling the contact number directly;
- 2) **Email:** interested participants can initially contact the study team through the study's email ([[contact]](mailto:[contact]));

- 3) **Study Website:** parents of interested participants can initially contact the study team through the study website (<http://smartstudy.web.unc.edu/parent-survey/>);

[figure not shown]
The study team will explain the study to interested parents and, with permission, arrange for the adolescent to complete the online screening, which includes the Quick Inventory for Depressive Symptomology (QIDS). Adolescents who meet pre-screen eligibility criteria (see [Section 4. Selection and Enrollment of Participants](#)) and their parent will then meet with a study team member to review study procedures in detail and provide informed consent and assent (see [Section 4.3: Study Enrollment Procedures](#) and [Section 6.2: Description of Evaluations](#)). Potentially eligible adolescents and a parent will then meet with the Study Psychologist for a clinical mental health assessment.

## 4. Selection and Enrollment of Participants

### 4.1: Inclusion Criteria

Participants must meet all of the inclusion criteria to participate in this study. Inclusion criteria for the study includes:

- Adolescents between ages 14-17. Adolescents may turn 18 after enrollment.

- Adolescents who are in high school.
- Adolescents with access to a smartphone or internet-enabled device.
- Adolescents and parent willing for their adolescent to be randomized to one of the two groups.
- Adolescent able to attend group sessions (8 weekly, 1.75 hour sessions; 6 monthly, 1.5 hour sessions) and complete study assessments.
- Adolescents experiencing subsyndromal depression assessed by:
  - Completion of screening questions by parent (see [Parent Screening Survey](#) and Telephone Consent);
  - Completion of QIDS by adolescent (see ;
  - Completion of clinical mental health assessment based on Diagnostic Interview Schedule for Children for Children (DISC-IV) by a study provider. The clinical mental health

assessment will screen for serious psychiatric illness, including major depression (MDD), suicidality, and other exclusion criteria.

Preliminary identification of subsyndromal depression will occur through screening questions completed by the parent (see Telephone Consent for details) and completion of QIDS by adolescent.

Adolescent and parent willing to receive a clinical mental health assessment, administered by a study provider, based on the Diagnostic Interview Schedule for Children-IV (DISC-IV) to screen for serious psychiatric illness, including major depression (MDD) and suicidality.

## 4.2: Exclusion Criteria

All candidates meeting any of the exclusion criteria at baseline will be excluded from study participation. Exclusion Criteria include:

- Adolescent and parent unable to speak, write, and read in English.
- Adolescents who have received prior mindfulness training (such as a mindfulness course).
- Adolescent unable or unwilling to attend or participate in group sessions and/or self-report assessments.
- Adolescents with the presence of suicidality or MDD as determined by clinical exam. Adolescents who have experienced MDD in the past will not automatically be excluded from the study.
- Adolescents with active substance abuse, defined as active treatment for substance abuse, legal consequences/school suspensions associated with substance use, or ongoing family conflict associated with substance use.
- Adolescents with a history of bipolar disorder, schizophrenia, severe autism/intellectual disability, or psychiatric hospitalization within the past 36 weeks. Milder forms of mental health and/or developmental disorders will not automatically constitute exclusion. The Study Psychologist will recommend exclusion only if the disorder would lead to disruption of the group process.
- Adolescents who currently or previously participated in a research intervention to address depression or psychiatric conditions. Adolescents are allowed to see their mental health provider while participating in the study.

## 4.3: Study Enrollment Procedures

We will recruit teens, ages 14-17, who are in high school and have subsyndromal depression, in several ways including:

- Emails with study information sent to the University community;
- Local guidance counselors made aware of the study;
- Flyers posted in the community and at local schools;
- In-person recruitment at local teen community organizations, churches, and school events (such as parent-teacher associations or parent-teacher organizations).

#### 4.3.1: Phone Screening and Psychological Exam

The study staff will contact interested parents and, with consent and assent, conduct an initial telephone screen with the adolescent. If still interested, materials will be sent to the parent to share with the adolescent, describing the study as two programs to help teens to reduce stress and feel more positive about themselves. Candidates will be given the QIDS assessment and if their score is at least 6, the teen and a parent will be eligible for a visit with the Study Psychologist for a clinical mental health assessment.

#### 4.3.2: Consenting

If a teen is eligible to participate based on the QIDS, the parent and teen will meet with a study team member to review study procedures in detail and provide written informed consent and assent. Any questions asked by the parent and or teen will be answered accordingly. They may decline, sign, or take the consent home with them to be signed later. The adolescent will be considered to be a subject after both the Informed consent is signed by the parent and the assent is signed by the teen.

At that time, if consented, the teen and parent will meet with the Study Psychologist for a psychological exam, including a face-to-face administration of the Diagnostic Interview Schedule for Children (DISC-IV). The clinical mental health assessment will determine continued eligibility.

#### 4.3.3: Documentation

The study team will maintain a screening log on REDCap (a secure, web-based research database) throughout the study. This will include names, dates of contact, and outcomes of the recruiting effort for each candidate. At all stages of the recruitment process, the study team will store any written documentation securely in locked study cabinets.

#### 4.3.4: Randomization

Although the study is not designed as an RCT, we do plan to test our randomization system. In all but the first two cohorts, as soon as 14-20 eligible adolescents qualify for enrollment, they will be allocated to one of the educational groups, using a specially-designed computer program (in REDCap). This program requires the operator to check off inclusion/exclusion criterion for each subject and confirm that subjects have been consented. The program utilizes a random-numbers generator with a permuted block design (blocks of 2 to 4) to ensure that the numbers of subjects allocated to the two arms over time are equal and to conceal the allocation. Randomization is stratified by gender.

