### 2.1: Background on Condition, Primary Study Focus

The rate of depression increases markedly over the course of adolescence. Currently 20-25% of adolescents experience a depressive episode before they graduate high school. In 2012 alone, 14% of girls and 5% of boys age 12-17 experienced a major depressive disorder, with only a third of those seeking treatment. Due to the number of adolescents untreated for symptoms, and the ability of these symptoms to interfere with developmental processes and lead to other clinical disorders, depression in adolescence increases the risk for maladaptive behaviors. Since depression often first appears in adolescence and unsuccessful treatment of adolescent depression increases the risk of chronic or recurrent depression in adulthood, managing depression symptoms at this critical stage of development can benefit mental health and functioning throughout the lifespan.

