## 9.2: Sample Size and Randomization

### 9.2.1: Treatment Assignment Procedures

Participants are randomized to treatment assignments to test the acceptability of randomization in the population. Random allocation, stratified by gender, is assured by a computer-generated assignment accessible to the REDCap administrator, but group assignment cannot be masked, except to quantitative data analysts.

**Power and sample size.** Untreated, >30% of adolescents are expected to develop incident depression. Power is calculated for time to incident MDD. With a sample size of 80, we expect to have 80% power to detect a hazard ratio of 0.52 for time to MDD between the groups. It is anticipated that we will screen 160 with the QIDS and 120 with the DISC to achieve a sample of 80 eligible teens (with 80 parents). Our target recruitment estimate is 53 females and 27 males, based on research demonstrating that there are twice as many female teens with subsyndromal depression as males. **Note that all enrollment figures refer to teens.** Each will have the involvement of one parent.

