### 9.5.2: Secondary Outcomes

For the secondary outcome, assuming feasibility is established, change in the Short Mood and Feelings Questionnaire (child and parent versions) will be examined in a linear regression in each condition, to test for any effect of either program. Then we will examine the change in depression scores through an

ANCOVA model controlling for baseline depression score and cohort to control for group specific effects. Subsequently, an exploratory analysis will examine the trajectory of changes over time by program arm, using graphical representations of outcomes at each time point by subject, cohort, and program arm as well as a longitudinal random effects model.

Hence, a within-group model would include terms for the follow-up depression score, the overall intercept, the cohort effect, the time effect, and a cohort\*time interaction—to allow the trajectory to vary by cohort—as well as random effects for individual subjects and subjects nested within cohorts. Between program arms, we would add terms for the program arm and its interaction with time.

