## Adolescent Demographic Questions

### Demographic questionnaire

Please circle the appropriate response to each question:

1. Your age:

14    15    16    17    18    19

2. Gender:

Male

Female

Male transitioning to female

Female transitioning to male

Unsure at this time

3. The race/ethnicity that you consider yourself:

Black    White    Asian    East Indian    American Indian    Pacific Islander    Latino/Hispanic    African    Other

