#### **8.4 Schedule and Content of Reports**

Recruitment, accrual, drop-out, and data quality evaluations are conducted prior to monthly Study Team Meetings. A report is given to each member of the study team. Reports are made to the ISMC after the first 20 subjects have completed the interventions and every six months thereafter. Accrual reports are made to NCCIH every 3-4 months and a comprehensive annual report is submitted annually.

Treatment assignment is arranged through a randomization protocol (stratified by gender) implemented by the study statistician in REDCap. Due to the nature of the interventions, it is unlikely that the research assistant or qualitative analysis will remain masked to assignment. However, the quantitative analysts should be able to remain masked and will analyze the data as two groups—group one and group 2.

The study database will be locked as soon as it is deemed to be completed. No interim analysis of quantitative data is planned. Qualitative data will be reviewed and coded as soon as it is available for use in improving the interventions.

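### Randomisation is stratified by gender, but none of the planned between-arm models includes the stratum; adding it is a small, nearly free improvement

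*Combined protocol and SAP*

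**What the plan says.** **Allocation.** Section 4.3.4: "Randomization is stratified by gender". Sections 3 and 9.2.1 repeat it, and DSMP section 8.4 describes a "randomization protocol (stratified by gender) implemented by the study statistician in REDCap". The levels of the stratifier are not listed in any of these places. Section 9.2.1 plans for two groups: "Our target recruitment estimate is 53 females and 27 males".

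**Analysis.**
- Section 9.5.1 (time to a PROMIS T-score of 70) plans Kaplan-Meier plots and Cox models and names no covariate or stratum. Section 9.6.1 restates only the Kaplan-Meier part.
- Section 9.5.2 (change in SMFQ) plans an "ANCOVA model controlling for baseline depression score and cohort to control for group specific effects".
- The longitudinal model in 9.5.2 and 9.6.1 has cohort, time, their interaction and random effects. For the arm comparison, 9.5.2 adds arm and arm by time. Gender does not appear.
- Section 9.5 limits every analysis to randomised teens who came to one or more classes, with no imputation.

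**Gender in the background.** Section 2.1 reports that in 2012 "14% of girls and 5% of boys age 12-17 experienced a major depressive disorder".

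**Gender on the forms.** The adolescent demographic questionnaire offers five answers: male, female, "Male transitioning to female", the reverse transition, and "Unsure at this time". DSMP section 4.1 shows that gender is also among the demographic items gathered at screening.

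**The concern.** A factor is usually chosen for stratification because it is expected to predict outcome. Stratified blocks remove some of the chance variation in the arm difference. An analysis that ignores the stratum still uses a variance that includes that variation, so the test tends to be slightly conservative. In a Cox model, leaving out a predictive factor also pulls the arm hazard ratio towards 1. Both effects cost some precision that the design has already paid for.

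The second issue is the analysis set. Blocks balance gender among those randomised. Once teens who never came to a class and those with missing outcomes are dropped, that balance may be lost. Adjusting for gender deals with a gender imbalance that arises this way. It does not deal with selective loss on other factors.

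What is at stake is the precision of exploratory arm comparisons meant to inform a larger trial, and how well this study models the analysis that trial would use.

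**Working it through.** **1. Models against the stratifier.**

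| Analysis | Terms named in the plan | Gender? |
|---|---|---|
| Kaplan-Meier and Cox (9.5.1, 9.6.1) | arm | no |
| ANCOVA (9.5.2) | baseline score, cohort | no |
| Longitudinal (9.5.2, 9.6.1) | cohort, time, cohort by time, random effects; arm and arm by time between arms (9.5.2) | no |

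**2. The plan's own figures.** The gender split adds up: 53 + 27 = 80, a ratio of 53/27 = 1.96. The stated 80% power at a hazard ratio of 0.52 with 80 teens does not reproduce. Schoenfeld's formula (two-sided 0.05, assumed because no alpha is stated) gives 4 × (1.960 + 0.842)² / (ln 0.52)² = 31.4/0.4276, which rounds up to 74 events. At a 30% control risk, expected events are 40 × 0.30 + 40 × (1 − 0.70^0.52) = 12.0 + 6.8 = 18.8, and power is about 29%. That is a separate matter, mentioned here only because it explains the low power levels below. The question for this point is how power changes.

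**3. How predictive gender might be.** The section 2.1 figures give a risk ratio of 14/5 = 2.8, or a hazard ratio of ln(0.86)/ln(0.95) = 0.1508/0.0513 = 2.94 if read as yearly risks. They describe the general population aged 12 to 17. Section 9.2.1 says subsyndromal depression is itself twice as common in girls. Dividing that out leaves roughly 2.8/2 = 1.4 among teens already selected for it. This is a crude figure, so I used 1, 2 and 2.94 as a range, with 2.94 as an upper bound.

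**4. Cost of leaving the stratum out.** The simulation had 53 girls and 27 boys, permuted blocks of 2 and 4 within gender, exponential event times and an arm hazard ratio of 0.52 (1 for type I error). It compared an unstratified with a gender-stratified log-rank test, two-sided 0.05, with 6,000 runs per setting. Monte Carlo error is about 0.6 points for power and 0.3 for type I error. The 30% control risk follows section 9.2.1; 50% is an assumed higher value.

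| Control risk | Gender HR | Power without / with stratum (%) | Change (points) | Type I without / with (%) |
|---|---|---|---|---|
| 30% | 1 | 28.1 / 28.2 | +0.1 | 4.9 / 5.0 |
| 30% | 2 | 27.1 / 27.7 | +0.6 | 5.1 / 5.4 |
| 30% | 2.94 | 28.1 / 29.6 | +1.5 | 4.5 / 5.2 |
| 50% | 1 | 44.0 / 43.7 | −0.3 | 5.4 / 5.3 |
| 50% | 2 | 43.5 / 44.8 | +1.3 | 4.8 / 5.5 |
| 50% | 2.94 | 41.0 / 44.9 | +3.9 | 4.1 / 5.3 |

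The crude value of 1.4 lies between the rows for 1 and 2, where the change runs from −0.3 to +1.3 points. The unstratified test falls clearly below 5% only when gender is strongly predictive and events are common.

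**5. Limits.** The simulation has no dropout, no cohort effect and no weekly grid of measurements, and it allocates all 80 teens by stratified blocks, although section 4.3.4 exempts the first two cohorts. The documents give no figure for how far gender predicts SMFQ change once baseline score is in the model, so the gain for the ANCOVA and longitudinal models cannot be computed.

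**The case against.** The best case against acting is that little is lost. Section 9.1 sets hypothesis testing aside, and 9.6.1 expects too little data to detect an effect. At the protocol's own risk level the gain is at most 1.5 points of power, and omission leaves the test valid, if anything cautious. The time-to-event outcome is a PROMIS threshold rather than diagnosed MDD, so the section 2.1 figures bear on it only indirectly. The ANCOVA already adjusts for baseline score, which should carry part of any gender difference. All of this stands, and it limits the point to a low-cost improvement.

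Two stronger readings are tempting and go beyond the documents:

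- *Some teens have no stratum.* A reader might infer this from five form answers against two planning groups. But nothing says the five-answer form feeds the REDCap allocation. Screening records gender too, with answer options that are not shown, and the 53/27 split is a recruitment estimate rather than a list of strata. What is missing is a description of the levels.
- *Allocation concealment is weakened because staff pick a stratum for some teens.* No passage describes such a choice. Table 3 puts demographics at Visit 1, before the randomisation step. Section 4.3.4 says the program conceals allocation, and section 6.2.2 assigns the step to a designated team member.

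**Conclusion.** The point holds as a minor improvement. Gender is the stratifier and none of the planned between-arm models uses it. Adding it would be expected to gain about 0 to 4 points of power in the time-to-event comparison, most likely near the lower end, and to remove a mild conservatism. It would also protect against gender imbalance arising in the analysed set. The size rests on an assumed gender hazard ratio between 1 and 2.94, control risks of 30% to 50%, and a two-sided 5% test.

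A reader might take section 2.1 to show that gender is strongly prognostic here, with a hazard ratio near 2.9. The documents do not support that. The percentages describe how many adolescents in the general population experienced MDD in one year. They are not incidence among teens selected for subsyndromal depression and free of MDD at entry. The case for adjustment rests on consistency with the design and on low cost.

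**What to change.** - **9.5.1:** fit the Cox model stratified by the gender variable used at randomisation, and say that the arm hazard ratio is conditional on gender. Kaplan-Meier plots by arm can stay as they are.
- **9.5.2 and 9.6.1:** add the same variable as a covariate in the ANCOVA and in the longitudinal model.
- **4.3.4 and 9.2.1 (supporting clarification):** name the field that drives the allocation, list its levels, and state how each of the five answers on the adolescent form maps to them, fixed before the randomise step opens. Section 9.5.1 describes the data as already collected. If allocation is complete, record the levels that were actually used.

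Make the analysis change while the quantitative analysts are still masked to arm (DSMP section 8.4). The cost is a few lines of text and about one degree of freedom in the ANCOVA and longitudinal models if the variable has two levels. With more levels the cost rises, and sparse strata would add little to the Cox model. If the sponsor prefers to leave the stratum out, one sentence giving the reason would be enough.
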